3.0 PATIENT ELIGIBILITY

3.1 Inclusion Criteria

- Histologically proven NSCLC, not classically deemed to be amenable to curative therapy based on disease extent at the time of diagnosis or disease progression after the initial diagnosis

[figure not shown]
- Age \geq 18 years
- Prior treatment with at least two lines of systemic therapy for advanced NSCLC, including one line of platinum-based combination chemotherapy
 - Treatment with concurrent chemotherapy and immunotherapy can count as two lines of therapy for the purposes of study eligibility.
- Radiological assessments, including CT within 21 days prior to study entry and PET/CT within 42 days prior to study entry, demonstrating measurable disease that includes at least one pulmonary or extrapulmonary lesion \geq 1 cm in greatest dimension that would be amenable to SBRT and at least one measurable lesion that would be outside of the SBRT treatment fields
- ECOG performance status 0-2
- Both men and women enrolled in this trial must agree to use adequate birth control measures during the trial and for at least 90 days after last receipt of study therapy. Patients and/or partners who are surgically sterile or postmenopausal are exempt from this requirement.
- The following laboratory results, within 21 days prior to study registration:
 - Hemoglobin \geq 9.0 g/dL
 - Absolute neutrophil count \geq 1.5 \times 10⁹/L
 - Platelet count \geq 100 \times 10⁹/L
 - Serum creatinine \leq 1.5 \times ULN OR creatinine clearance (by Cockcroft-Gault formula) $>$ 60 mL/min
 - AST and ALT \leq 2.5 \times ULN
 - Total bilirubin \leq 2.0 \times ULN (except patients with Gilbert's syndrome, who must have a total bilirubin \leq 3.0 mg/dL)
 - Negative SARS-CoV-2 (COVID-19) PCR test
 - COVID-19 testing may be repeated periodically based on institutional policies and must be repeated for any subject with unexplained signs (e.g., imaging findings, fever) or symptoms (e.g., anosmia) concerning for COVID-19 infection or with recent known exposure to COVID-19.

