4.2 Study Calendars

4.2.1 Pre-Registration and Pre-treatment Assessments

	Timing
CBC, BMP, LFTs	Within 21 days prior to study entry
Amylase, Lipase	Pre-treatment
Negative SARS-CoV-2 PCR	Within 21 days prior to study entry
PET/CT	Within 42 days prior to study entry
CT C/A/P	Within 21 days prior to study entry
QoL Assessments	Pre-treatment
Correlative Study Blood Draw	Pre-treatment ¹
CDX-301 ADA and CDX-1140 PK	Pretreatment (Arm 1 only) ¹

1. Must be obtained at least 21 days after last receipt of chemotherapy, targeted cancer therapy, immunotherapy, radiotherapy (excluding palliative radiotherapy), or major surgery.

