4.2.2 Arm 1 (experimental study arm)

ARM 1	Week 1	Week 2	Week 4	Week 6	Weeks 9 ¹ , 17 ² , 25 ² , 33 ² , 41 ² , 49 ²
History and Physical Examination	X	X ⁵ X ⁶	X	X ⁵ X ⁶	X
CBC, BMP, LFTs, Amylase, Lipase	X	X ⁵ X ⁶	X	X ⁵ X ⁶	X
Activity Data Download ³	X	X	X	X	X
QoL Assessments		X	X	X	X
Correlative Study Blood Draw		X ⁷		X ⁷	X
CDX-301 ADA and CDX-1140 PK		X ⁷ X ⁸ X ⁶		X ⁷ X ⁶	
CT C/A/P					X
Stereotactic Radiotherapy (SBRT) ⁴	XXX				
FLT3 Ligand (CDX-301)	XXXXX				
CD40 Agonist Antibody (CDX-1140)		X		X	

1. +/- 1 week

2. +/- 2 weeks

3. For subjects who opt to participate in this part of the study

4. SBRT should be delivered in 1, 3, or 5 fractions per target and may continue beyond Week 1 when treating multiple sites.

5. On the day of CDX-1140 infusion

6. One day after CDX-1140 infusion

7. Immediately before CDX-1140 infusion

8. 2 hours after CDX-1140 infusion

Cycles of SBRT(to an untreated lesion)+CDX-301+CDX-1140 may be repeated.

- At least 8 weeks must separate the start of each treatment cycle.
- CDX-1140 may be omitted from retreatment cycles for subjects with prior DLT or intolerable toxicity attributed to CDX-1140.
- The schedule of assessments will reset when a new cycle is initiated.

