4.2.3 Arm 2 (control arm)

ARM 2	Week 1	Week 2	Week 4	Week 6	Weeks 9 ¹ , 17 ² , 25 ² , 33 ² , 41 ² , 49 ²
History and Physical Examination	X	X	X	X	X
CBC, BMP, LFTs, Amylase, Lipase	X	X	X	X	X
Activity Data Download ³	X	X	X	X	X
QoL Assessments		X	X	X	X
Correlative Study Blood Draw		X		X	X
CT C/A/P					X
Stereotactic Radiotherapy (SBRT) ⁴	XXX				

1. +/- 1 week

2. +/- 2 weeks

3. For subjects who opt to participate in this part of the study

4. SBRT is only required for subjects with limited disease burden.

SBRT should be delivered in 1, 3, or 5 fractions per target and may continue beyond Week 1 when treating multiple sites.

Standard systemic therapy may be administered at any time for subjects with extensive disease burden and any time after completion of all planned SBRT for subjects with limited disease.

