5.2.2 Treatment Schedule

CDX-301 and CDX-1140 will only be administered to subjects on Arm 1. Subjects on Arm 2 will not “crossover” if disease progression is observed. The Study Calendar (Section 4.2) describes the timing of study drug administrations.

Some subjects on Arm 1 may receive more than one “cycle” of CDX-301, CDX-1140, and SBRT (targeting a lesion not previously treated with SBRT). The decision to administer treatment cycles beyond cycle 1 must be agreed upon by the treating physicians, the principal investigators, and the study subject. Additional treatment cycles will not be offered to subjects who develop disease progression within four months of receiving a previous cycle of study therapy or to subjects who have no evidence of active disease. Subjects who previously experienced DLT or intolerable toxicity related to CDX-1140 may be treated with CDX-301 and SBRT and without CDX-1140 in subsequent treatment cycles.

For subjects who receive more than one cycle of study therapy, the schedule of events will reset at the beginning of each cycle. At least 8 weeks must separate the start of each treatment cycle.

CDX-301

Five injections of CDX-301 should be administered daily during Week 1 (Monday-Friday) of a treatment cycle. If that is not possible due to department closure for a national holiday, inclement weather, or another reason that is not treatment-related toxicity, CDX-301 treatment may extend to Week 2 (though not beyond 10 days after the first CDX-301 dose).

CDX-1140

The first CDX-1140 will take place 4 days (+/- 1 day) after the last dose of CDX-301. As CDX-301 will typically be given from Monday-Friday, CDX-1140 will usually be given on a Tuesday. The second dose of CDX-1140 will be given 4 weeks (+/- 3 days) after the first CDX-1140 dose. CDX-1140 will not be administered on a Friday, as a clinic visit the day after each CDX-1140 dose is required.

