There are data showing that prophylactic treatment with rhuFlt3L can prevent or abrogate leukemic activity⁹⁷. There also are data showing the expression of Flt3 and the Flt3L receptor, on some leukemias, and extensive data that support an association between an increase in proliferation or suppression of apoptosis in clinical leukemias that bear constitutively activated Flt3 mutations. These mutations do not appear to be causal for AML⁹⁸⁻¹⁰¹. It is not known whether the addition of rhuFlt3L to patients with leukemia expressing Flt3 will promote leukemic proliferation, or whether the ligand can promote the development of leukemia in people without pre-existing leukemia. Since the effect of administered rhuFlt3L is transient, it would seem unlikely to have any persistent effects and no cases of leukemia were reported after rhuFlt3L administration in previous studies.

Pregnancy, Carcinogenesis, and Teratogenicity

The effects of CDX-301 on fertility, pregnancy, or the unborn fetus have not been determined. It is not known if CDX-301 is excreted in milk or can cross the placenta. For this reason, pregnant and nursing women should not receive CDX-301. Women of childbearing potential treated with CDX-301 must take adequate contraceptive measures.

CDX-1140

Most side effects associated with CDX-1140 to date have occurred in the 24-48 hours following the CDX-1140 infusion, been mild to moderate, and have resolved with or without medications such as acetaminophen, NSAIDS, and/or anti-nausea medication. In a few cases, the side effects have been severe and have required hospitalization and treatment with corticosteroids or other immunosuppressive medications. Treatment related adverse events that have occurred in > 10% of patients include fatigue, arthralgia, nausea, chills, fever, diarrhea, myalgia, vomiting, AST increase, and ALT increase.

Cytokine Release Syndrome

2 patients who received CDX-1140 monotherapy and 4 patients who received CDX-1140 in combination with CDX-301 have experienced cytokine release syndrome. Symptoms included fever, hypotension, hypoxia, fatigue, headache, and nausea.

Pneumonitis

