- Prophylactic premedication is required prior to CDX-1140 administration: diphenhydramine 25/50 mg (or equivalent anti-histamine), 500 to 750 mg paracetamol (acetaminophen), and naproxen sodium 250 mg (or equivalent NSAID) at least 30 minutes prior to CDX-1140 administrations. Ranitidine 150 mg (or equivalent) may also be incorporated into the premedication regimen. Prophylactic premedication with corticosteroids is to be avoided because of the potential to attenuate the anti-tumor activity of CDX-1140.
- Post-infusion medication is required following CDX-1140 administration: In the 24-48 hours following the CDX-1140 infusion, alternate oral acetaminophen (1000 mg) and non-steroidal anti-inflammatory (e.g., ibuprofen 200 mg) q6H. An anti-histamine and anti-emetic may also be utilized if clinically indicated. Patients should be evaluated to determine if continuation of post-infusion medication is needed when they are seen on the Cycle 1 Day 2 visit. Note, the potential for toxicity with these drugs and appropriate precaution should be utilized in patients with risk factors for toxicity, e.g. patients with peptic ulcers, increased LFTs, or increased creatinine. Also, care should be taken to mediate for no longer than is necessary in order to avoid

potential confounding factors in determining adverse event causality (e.g. increased LFTs).

- The effect of CDX-1140 on the absorption, metabolism, or excretion of other drugs has not been studied. As CDX-1140 is a human monoclonal antibody, inhibition or induction of cytochrome P450 (CYP) enzymes or other typical drug metabolizing enzymes is unexpected, and thus, interaction with other medications metabolized through these pathways is unlikely.
- For patients in Part 2, concomitant administration of CDX-301 with growth factors such as G-CSF should be done with caution and the CBC followed closely.

6.0 STUDY THERAPY – ARM 2

Stereotactic Body Radiotherapy for Limited Disease

Subjects on Arm 2 with “limited disease”, as defined in Section 5.1.1, will be treated with SBRT to all sites of known active disease. SBRT details are provided in Section 5.1. SBRT will be delivered in the same fashion for both study arms.

Other radiotherapy

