8.0 STATISTICAL CONSIDERATIONS

8.1 Randomization Procedure

At the time of study registration, subjects will be stratified by EGFR/ALK mutation status and disease burden and then will be randomized 1:1 between the two study arms using a modified permuted block treatment allocation scheme¹¹⁵. Block sizes of 2 (65%) and 4 (35%) will be considered. Study subjects and study personnel will NOT be blinded with respect to the randomization result.

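### The bar on CDX-301 in pregnant and nursing women is not carried into eligibility, and no pregnancy test is required before randomisation or the first dose

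*Combined protocol and SAP*

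**What the plan says.** The safety rule stands in Section 5.2.6, in the CDX-301 precautions: "pregnant and nursing women should not receive CDX-301". The reason given there is that effects on fertility, pregnancy and the fetus are not established, and that passage across the placenta or into milk is unknown. The same paragraph requires contraception in women of childbearing potential who are treated with CDX-301. The CDX-1140 part of Section 5.2.6 makes no statement about pregnancy.

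The closest eligibility item is in Section 3.1. Men and women "must agree to use adequate birth control measures during the trial and for at least 90 days after last receipt of study therapy", with an exemption for those who are surgically sterile or postmenopausal. Section 3.2 lists no exclusion for pregnancy or nursing.

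Section 4.2.1 sets the entry tests; the blood counts and chemistry are timed "Within 21 days prior to study entry". It includes no pregnancy test, and neither do the on-study calendars for Arm 1 (4.2.2) and Arm 2 (4.2.3). Arm 1 subjects may be retreated, and the calendar then restarts: "The schedule of assessments will reset when a new cycle is initiated".

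Allocation is made at registration. Section 8.1 says: "At the time of study registration, subjects will be stratified by EGFR/ALK mutation status and disease burden", and randomisation follows. Section 4.1 keeps all 46 subjects in the efficacy analyses.

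**The concern.** A rule that certain patients must not receive a drug works only if something in the enrolment process identifies them. Here the rule appears only as a drug precaution, while the eligibility criteria and calendars that sites apply at entry are silent. Two situations should be kept apart.

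- **Known pregnancy or nursing.** Section 5.2.6 already bars CDX-301. The weakness is one of placement: the bar applies at dosing, after allocation, when it should apply before randomisation.
- **Unrecognised pregnancy.** No step in the protocol requires anyone to look for it. This is the substantive gap.

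What is at stake is patient and fetal safety. One Arm 1 cycle comprises five CDX-301 injections, two CDX-1140 infusions and SBRT. There is also a smaller design consequence. If a pregnancy is recognised only after allocation to Arm 1, the subject cannot receive CDX-301 but remains in the efficacy analysis.

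**Working it through.** The plan gives no figure on this point, so the check is a comparison of texts followed by a short calculation of scale.

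**1. Where could the rule be put into effect?** I counted the items in each list that a site would use at entry or on study.

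| Place | Items | Items on pregnancy or nursing |
|---|---|---|
| Section 3.2, trial exclusions (a 13th bullet concerns activity monitoring only) | 12 | 0 |
| Section 3.1, entry laboratory results | 7 | 0 |
| Section 4.2.1, calendar rows | 8 | 0 |
| Section 4.2.2, calendar rows | 10 | 0 |
| Section 4.2.3, calendar rows | 7 | 0 |

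The calendars together have 8 + 10 + 7 = 25 rows, none of them relevant. The seven laboratory items are haemoglobin, neutrophils, platelets, creatinine or its clearance, AST and ALT, bilirubin, and the SARS-CoV-2 PCR.

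**2. Does the birth-control criterion fill the gap?** No. It asks for an undertaking about conduct during the trial and for 90 days after study therapy. A woman already pregnant, and unaware of it, can give that undertaking truthfully. The criterion does not address nursing. Its exemption for sterile and postmenopausal patients implies that women of childbearing potential can enrol.

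**3. Do routine visits fill it?** Not by requirement. The calendars schedule a history and physical examination in Week 1 without mentioning pregnancy, and Section 7.1 permits it to be done remotely.

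**4. Is it the plan's usual practice to leave such precautions outside eligibility?** No. Autoimmune disease, FLT3 mutation and thrombosis are all discussed in Section 5.2.6 and all have related exclusions in Section 3.2. Pregnancy and nursing carry an explicit bar and have none. No reason is given.

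**5. Does it matter in both arms?** Eligibility is applied before the arm is known, so a single criterion has to serve both. Section 11.0 also counts radiotherapy, together with CDX-301 and CDX-1140, as study treatment. In Arm 2, "SBRT is only required for subjects with limited disease burden", but Section 6.0 says that those subjects "will be treated with SBRT to all sites of known active disease". Section 5.1.5 allows abdominal and pelvic targets at 15 Gy x 3.

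**6. How many subjects?** Inputs: 46 subjects in total (Section 4.1) and 23 in Arm 1 (Section 8.2). The share of women of childbearing potential is not in the documents; I assume 2% to 15%.

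- All subjects: 0.02 x 46 = 0.92 and 0.15 x 46 = 6.9, or about 1 to 7.
- Arm 1: 0.02 x 23 = 0.46 and 0.15 x 23 = 3.45, or about 0.5 to 3.5.

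These are numbers of enrolled women who would be tested. The number with an unrecognised pregnancy would be a further fraction of them, which the documents give no means of estimating.

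**The case against.** The strongest reply is that the protocol already bars CDX-301 in pregnancy and nursing and requires contraception of everyone enrolled, so that little is left uncovered, in a population where few women will be of childbearing potential. That is right for known cases and for conception during the trial. It does not cover a pregnancy that exists and is unrecognised at entry.

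A second reply is that the documents reviewed are incomplete. Section 5.2.4 names the Investigator Brochures as the reference for safety information, and neither they nor the consent pages were available. Either might require a test, and the silence on CDX-1140 in Section 5.2.6 does not show that no precaution exists for that drug. I therefore put little weight on CDX-1140. A requirement held elsewhere would still need to appear in Sections 3 and 4.2 to operate at enrolment.

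Third, the 2% to 15% range has no source in the documents and counts tests, not pregnancies. That is so; it indicates scale only, and the finding does not depend on it. Patients who are screened but not enrolled would add a few tests.

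Fourth, a repeat test before later cycles is less compelling. Retreatment needs agreement from the treating physicians, the principal investigators and the subject, and contraception is mandatory throughout. I accept that this part is secondary: the remaining risk is contraceptive failure or non-adherence. It is not nil, because under Section 5.2.2 "At least 8 weeks must separate the start of each treatment cycle", which leaves time for a pregnancy to begin between cycles.

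**Conclusion.** The concern holds. The protocol states a clear bar on CDX-301 in pregnant and nursing women, yet no eligibility criterion, entry test or calendar row puts it into effect, and a woman with an unrecognised pregnancy could be randomised and treated without any departure from the written procedures. The change should be made. The number affected is probably small: about 1 to 7 women to be tested among 46, on an assumed share, and fewer pregnancies than that. The conclusion rests on the text of Sections 3.1, 3.2, 4.2 and 5.2.6, and on no overriding requirement in the consent form or the Investigator Brochures. If one exists, the remaining task is to bring it into the protocol. Sample size, alpha, power and the PFS comparison are unaffected.

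**What to change.** 1. In Section 3.2, exclude women who are pregnant or nursing, in both arms.
2. In Sections 3.1 and 4.2.1, require a negative serum or urine pregnancy test in women of childbearing potential before registration. The 21-day window used for the other entry laboratory tests is the simplest choice. A shorter window, or a repeat shortly before the first CDX-301 dose, is better, because a test taken 21 days before registration is older still by the time treatment starts.
3. Secondarily, in Section 4.2.2, add a repeat test before the first CDX-301 dose of each later cycle.

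The cost is one exclusion line, one inclusion line and one row in Section 4.2.1, with one further row in Section 4.2.2 if item 3 is adopted. In practice it means one routine test per entry or cycle in a probably small number of women, which can be run with blood already being drawn. The sample size and the analyses do not change.

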5.2.7 Concomitant Therapy

Subjects may continue to use any ongoing medications not prohibited by the inclusion/exclusion criteria. However, efforts should be made to maintain stable doses of concomitant medications during study treatment. Subjects must be instructed not to take any medications, including over-the-counter products, without first consulting with the investigator.

Investigators may prescribe concomitant medications or treatments deemed necessary to provide adequate supportive care. However, while on study, when clinically appropriate, subjects should strictly follow the study-prescribed treatment regimen in accordance with the following guidance:

- Concurrent administration of any anticancer therapies and/or other investigational agents are prohibited throughout the treatment period.
 - Following treatment, but prior to documented progression of disease, additional anticancer therapies should be avoided if clinically feasible. If additional anticancer therapies are needed, it should be discussed and agreed upon with the Principal Investigator prior to administration.
 - Following progression of disease, subjects may receive any appropriate alternate therapies.
- During study treatment, subjects may receive supportive care to include bisphosphonates, hematologic, and anti-infectious support and pain management.
- Thoracentesis or paracentesis may be performed if needed for comfort. If surgical intervention or localized radiation become indicated (either for palliation or down-staging of previously non-resectable tumor), these interventions are permitted, but should be avoided if clinically feasible until after the second response assessment, following consultation with the Principal Investigator. A tumor response assessment should be conducted prior to any intervention, in order to document progression and/or confirm an objective response. Subjects who undergo surgical resection or radiation in the absence of progression may continue to receive study treatment until remaining lesions meet criteria for progression of disease. Platelet counts should be checked immediately before any invasive intervention, as CDX-1140 may a decrease in platelet count in the days following each infusion.
- Immunosuppressive agents are prohibited during the study, with the following exceptions:

- Immunosuppressive agents and the use of systemic corticosteroids are permitted in the context of treating AEs. Subjects receiving corticosteroids for treatment of drug-related AEs must be at \leq 10 mg/day prednisone or equivalent prior to re- initiation of study therapy.
- Subjects are permitted the use of topical, ocular, intra-articular, intranasal, and inhalational corticosteroids (with minimal systemic absorption).
- Vaccinations:
 - Non-study vaccinations are prohibited until at least 28 days after the last dose of CDX-301. Otherwise, any vaccination containing live, attenuated, or inactivated virus may be permitted if clinically indicated. However, this must be discussed with the Principal Investigator prior to administration and may require a study drug washout period prior to and after administration of the vaccine. Inactivated influenza vaccination is permitted on study without restriction.
 - Some of the systemic adverse events attributed SARS-CoV2 vaccines, such as fever, fatigue, arthralgias, and myalgias, overlap with the adverse events associated with CDX-1140. Administration of the SARS-CoV2 vaccine in close temporal association with CDX-1140 may confound causality assessments for any accompanying adverse events. Therefore, administration of the SARS-CoV2 vaccination and CDX-1140 should be separated by at least 1 week, if possible. For CDX-301, if possible, the vaccine should be administered either at least 1 week prior to the initiation of CDX-301 or at least 3 weeks after the first dose in a cycle, and if eligible for another cycle of treatment, at least 1 week prior to the next cycle. The recommendation is based on the biological activity of CDX-301, which induces a transient increase in hematopoietic cells, including dendritic cell, that peaks at approximately 2 weeks from the initiation of treatment and then rapidly declines. No data is available on the potential impact of CDX-1140 or CDX-301 on the immunogenicity or adverse event profile of the SARS-CoV2 vaccines, therefore decisions to vaccinate patients while participating in this study will be individualized and based on the judgement of the treating investigator.
- Prophylactic premedication is required prior to CDX-1140 administration: diphenhydramine 25/50 mg (or equivalent anti-histamine), 500 to 750 mg paracetamol (acetaminophen), and naproxen sodium 250 mg (or equivalent NSAID) at least 30 minutes prior to CDX-1140 administrations. Ranitidine 150 mg (or equivalent) may also be incorporated into the premedication regimen. Prophylactic premedication with corticosteroids is to be avoided because of the potential to attenuate the anti-tumor activity of CDX-1140.
- Post-infusion medication is required following CDX-1140 administration: In the 24-48 hours following the CDX-1140 infusion, alternate oral acetaminophen (1000 mg) and non-steroidal anti-inflammatory (e.g., ibuprofen 200 mg) q6H. An anti-histamine and anti-emetic may also be utilized if clinically indicated. Patients should be evaluated to determine if continuation of post-infusion medication is needed when they are seen on the Cycle 1 Day 2 visit. Note, the potential for toxicity with these drugs and appropriate precaution should be utilized in patients with risk factors for toxicity, e.g. patients with peptic ulcers, increased LFTs, or increased creatinine. Also, care should be taken to mediate for no longer than is necessary in order to avoid

potential confounding factors in determining adverse event causality (e.g. increased LFTs).

- The effect of CDX-1140 on the absorption, metabolism, or excretion of other drugs has not been studied. As CDX-1140 is a human monoclonal antibody, inhibition or induction of cytochrome P450 (CYP) enzymes or other typical drug metabolizing enzymes is unexpected, and thus, interaction with other medications metabolized through these pathways is unlikely.
- For patients in Part 2, concomitant administration of CDX-301 with growth factors such as G-CSF should be done with caution and the CBC followed closely.

6.0 STUDY THERAPY – ARM 2

Stereotactic Body Radiotherapy for Limited Disease

Subjects on Arm 2 with “limited disease”, as defined in Section 5.1.1, will be treated with SBRT to all sites of known active disease. SBRT details are provided in Section 5.1. SBRT will be delivered in the same fashion for both study arms.

Other radiotherapy

Subjects on Arm 2 with disease that is not amenable to comprehensive SBRT may be treated with any form of palliative radiotherapy, including SBRT, to address symptoms or prevent symptom progression. Treatment details will be left to the discretion of the managing physicians but are expected to align with institutional standards and established guidelines^{75,106}.

Systemic therapy

Subjects on Arm 2 with extensive disease burden are expected to receive a standard treatment regimen. Approved options at this time include docetaxel (+/- ramucirumab), pemetrexed, and gemcitabine⁷⁵. Selection of the systemic treatment regimen will be left to the discretion of the treating physician. Assessments for subjects receiving standard systemic therapy should follow the Study Calendar (Section 4.2).

Subjects on Arm 2 with limited disease may receive systemic therapy after completion of SBRT or may undergo surveillance without active therapy. Systemic therapy should not be initiated until all planned SBRT is completed.

